3.2 Derivation of safety variables

3.2.1 Exposure to IP and treatment compliance

Extent of exposure to IP is defined as the number of days between the date of first dose of IP in the predecessor study and the date of last dose of IP inclusive plus the number of days allowance for the dosing interval that is:

Extent of exposure (days) = [minimum (date of last dose of IP + 33 days; date of death; date of study withdrawal) - date of first dose of IP in the predecessor study] + 1

The extent of exposure will be calculated separately for exposure to tezepelumab and exposure to placebo, so in the above calculation, the extent of exposure to placebo will be based on the first and last dose of placebo, reflecting that the last dose of placebo may be in the predecessor study despite the subject continuing to be dosed in the LTE study. Similarly, the extent of exposure to tezepelumab for the All Tezepelumab treatment group will be based on the first and last dose of tezepelumab, reflecting that the first dose of tezepelumab will be during the LTE study for some subjects.

The above calculation does not consider any gaps in exposure caused by the subject missing one or more intermediate scheduled 4-weekly doses. Such cases will be identified in the CSR if they occur but will not explicitly be accounted for in any analysis.

Extent of exposure will also be calculated separately for the predecessor and LTE period, using only dates from the corresponding period as defined for the on-treatment period in Section 3.1.5.1. If the last date of predecessor period is on the same date as the first date of LTE period, then the date will be counted in both periods. However, it will be only counted once for the overall extent of exposure using the formula above.

The total subject-years exposure for a treatment group will be derived as the sum of the individual subject extents of exposure (days) for that treatment group and divided by 365.25.

Treatment compliance will be calculated as follows:

Treatment compliance (%) = $[(Total\ number\ of\ actual\ dosing\ occasions/total\ number\ of\ expected\ dosing\ occasions)] \times 100\%$

In order to allow for subjects who discontinue IP early in the compliance calculation, the number of expected dosing occasions will be calculated as the number of scheduled dosing visits up to and including the last available dosing visit for that subject.

Treatment compliance will also be calculated separately for the predecessor and LTE periods.

3.2.2 Adverse events – general

Adverse events (AEs) experienced by any subject at any time during the entire study will be coded using the latest version of the Medical Dictionary for Regulatory Activities (MedDRA) at the time of the primary database lock. This version of MedDRA will also be used during the final database lock.

AEs will be categorised for analysis according to their onset date into the following study periods for the SAF and SAF-LTE analysis sets:

- AEs occurring during screening/run-in period: date of Visit 1 in the predecessor study ≤
 AE onset date < date of first dose of IP in the predecessor study
- AEs occurring during on-treatment period: date of first dose of IP \leq AE onset date \leq minimum (date of last dose of IP + 33 days, date of death, date of study withdrawal)
- AEs occurring during post-treatment/follow-up period (for subjects still being followed up then): date of last dose of IP + 33 days < AE onset date ≤ study completion or withdrawal date
- AEs occurring during on-study period: date of first dose of IP ≤ AE onset date ≤ study completion or withdrawal date.

In addition, AEs will be further categorised for analysis for the on-treatment and on-study periods by the predecessor and LTE time periods as defined in Section 3.1.5.1.

If the AE has a completely missing (and unresolvable) onset date, then the AE will be assumed to have occurred during the on-treatment period, unless the end date indicates unambiguously that the AE resolved before treatment started. If the AE has a partially missing (and unresolvable) onset date, then the AE will also be assumed to have occurred during the on-treatment period, unless either the end date indicates unambiguously that the AE resolved before treatment started, or the partial onset date is in the month/year prior to start of treatment.

For each treatment group, exposure adjusted incidence rates will be defined as the number of subjects reporting adverse events divided by total exposure duration for that treatment group.

For individual subjects, exposure duration (days) for each time period is derived using the start date and end date defined for the on-treatment and on-study period in Section 3.1.5.1. The total exposure duration (years) for a treatment group will be derived as the sum of the individual subject exposure duration (days) for that treatment group and divided by 365.25.

In all incident rate summaries of AEs, multiple occurrences of the same event for a particular subject will not be counted as separate events. A subject will either be considered to have no events of the type being summarised, or one or more occurrences of that event.

Furthermore, for specific AEs, exposure adjusted occurrence rates will be defined as the number of events divided by total exposure duration for that treatment group, as described above.

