2.1.2 Treatment groups

There are 5 possible groupings across the predecessor and LTE studies as shown in Figure 2 below.

Figure 2 Treatment groupings

[figure not shown]

Note: Groups 2 and 5 reflect subjects in the predecessor studies who do not enrol in the LTE study.

The following treatment groups for analyses will be considered, where time from first dose is applicable for the safety analysis, and time from randomisation is applicable for the efficacy analysis:

Primary (based on the SAF and FAS analysis sets):

[figure not shown]
- Randomised Tezepelumab (Rand Teze): All subjects originally randomised to tezepelumab in the predecessor studies. Will include all data from first dose/randomisation in the predecessor studies to end of the LTE study. (A, B and C)
- Randomised Placebo (Rand Pbo): All subjects originally randomised to placebo in the predecessor studies. Will include all data from first dose/randomisation in predecessor studies up until switch to tezepelumab, and all data from first dose/randomisation in the predecessor studies to end of the LTE study for subjects randomised to placebo in the predecessor studies and the LTE study. (D, F, G and H)

Supportive (based on the SAF-LTE and FAS-LTE analysis sets):

[figure not shown]
- Tezepelumab Predecessor+Tezepelumab LTE (Teze+Teze): All subjects originally randomised to tezepelumab in the predecessor studies and re-randomised to tezepelumab in the LTE study. Will include all data from first dose/randomisation in the predecessor study to end of the LTE study for only subjects enrolled into the LTE study. (A and B)
- Placebo Predecessor+Placebo LTE (Pbo+Pbo): All subjects randomised to placebo in the predecessor studies, and later re-randomised to placebo in the LTE study. Will

include all data from first dose in predecessor studies until end of the LTE study for only subjects enrolled into the LTE study. (F and G)

[figure not shown]
Supportive (for exposure summaries and rare events based on the SAF analysis set):

[figure not shown]
• All Tezepelumab (All Teze): All subjects randomised to tezepelumab in the predecessor studies and subjects randomised to tezepelumab in the LTE study. It will include all data from time of first dose/randomisation to tezepelumab. (A, B, C and E)

Additional (for the assessment of durability of benefit based on the SAF-LTE and FAS-LTE analysis sets):

- Tezepelumab Predecessor+Tezepelumab LTE (Teze+Teze): as defined above

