If the medication record has a completely missing onset date, the subject will be assumed to have been on the medication on the date of the first study procedure. If the medication record has a partially missing onset date (month/year or year only) which is the same as that for the end of IP treatment, it will be assumed to have started on-treatment. If the medication record has a partially missing onset date (month/year or year only) which is the same as that for the start of IP treatment, it will be assumed to have started before treatment.

If the medication record has a completely missing end date, the subject will be assumed to have been on the medication on the date of study completion or withdrawal. If the medication record has a partially missing end date (month/year or year only) which is the same as that for start of IP treatment, it will be assumed to have ended on-treatment. If the medication record has a partially missing end date (month/year or year only) which is the same as that for end of IP treatment, it will be assumed to have ended post-treatment.

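### An AE with a partial onset date is classed as on-treatment even when its known month and year lie wholly after the on-treatment period

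*SAP*

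**What the plan says.** SAP 3.2.2 sorts AEs by onset date. A dated AE is on-treatment from first dose up to the "minimum (date of last dose of IP + 33 days, date of death, date of study withdrawal"). After last dose plus 33 days it belongs to the post-treatment/follow-up period.

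A separate rule applies "If the AE has a partially missing (and unresolvable) onset date". The default is that "then the AE will also be assumed to have occurred during the on-treatment period". Two exceptions follow:

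- "the end date indicates unambiguously that the AE resolved before treatment started"
- "the partial onset date is in the month/year prior to start of treatment"

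The rate denominator in the same section is exposure time cut at the start and end dates of the relevant period. Protocol 9.4.2 assesses the primary objective through on-treatment AEs, AESIs and SAEs. SAP 4.5.1 tabulates each AESI category for the on-treatment period only. Post-treatment AEs are marked in a listing but not summarised separately.

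SAP 3.1.7, on medications, does look at the end of treatment: a partial onset date "which is the same as that for the end of IP treatment, it will be assumed to have started on-treatment".

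**The concern.** A default to on-treatment is sensible when timing is unknown. Here it also applies when timing is known well enough to rule on-treatment onset out. If the record holds a month and year that start after the on-treatment period has ended, the rule overrides them. The event joins the on-treatment numerator while the time in which it arose is absent from the denominator.

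The most exposed subjects are those who stop investigational product early and remain in follow-up. Under protocol 7.1.1 some are followed by monthly telephone calls, or by a single call at Week 104 after the 16-week visit, and AEs are collected on those calls. Imprecise onset dates are plausible there, although that is an inference and not something the documents state. The stake is modest for common AEs. It is greater for a rare AESI, such as a malignancy or severe infection, where the count may be very low.

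**Working it through.** No figure in the plan depends on this rule, so there is none to reproduce. The check has two parts.

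**1. The rule beside the period definitions in SAP 3.2.2**

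| What is known about onset | Class |
|---|---|
| Full date, before first dose | Screening/run-in |
| Month/year before treatment start | Excepted from on-treatment |
| Full date, after last dose + 33 days | Post-treatment |
| Month/year wholly after last dose + 33 days | On-treatment (no exception applies) |

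Rows three and four describe the same event recorded with different precision, yet they receive different classes. Rows one and two agree with each other. The inconsistency exists only at the end of treatment.

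**2. Size, as an illustration**

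Inputs:
- Target days from SAP Table 3: Week 52 = 365, Week 64 = 449, Week 76 = 533, Week 100 = 701, Week 104 = 729, Week 116 = 813.
- On-treatment allowance: 33 days (SAP 3.2.2).
- Share of AEs with a partial onset date, f: not in the documents; assumed 1%, 5% or 10%.
- Assumed constant AE rate, and the same f on and off treatment.

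Formula: relative inflation of the on-treatment event count = f × (misassigned days ÷ on-treatment days).

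*Completer.* Last dose is on day 701, so on-treatment ends on day 701 + 33 = 734. Follow-up to day 813 leaves 813 − 734 = 79 post-treatment days. Averaged over all possible calendar positions of the end date, about 64.3 of these 79 days (range 49 to 79) fall in months wholly after it. Then 64.3 ÷ 734 = 0.0876, giving:
- f = 1%: 0.09%
- f = 5%: 0.44%
- f = 10%: 0.88%

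*Subject who stops during the LTE and is followed to Week 104.* All days up to day 729 are counted, including the rest of the month in which on-treatment ends, so these are upper bounds.

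| Last dose | On-treatment ends | Days to day 729 | Ratio | f = 1% / 5% / 10% |
|---|---|---|---|---|
| Week 52 | 365 + 33 = 398 | 331 | 331/398 = 0.83 | 0.8% / 4.2% / 8.3% |
| Week 64 | 449 + 33 = 482 | 247 | 247/482 = 0.51 | 0.5% / 2.6% / 5.1% |
| Week 76 | 533 + 33 = 566 | 163 | 163/566 = 0.29 | 0.3% / 1.4% / 2.9% |

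For the Week 64 case, 247 days is about 35 of the 40 weeks between Week 64 and Week 104. These percentages apply to that subject's own expected count, not to the arm. The assumed dropout rates are blacked out, so an arm-level figure cannot be built from the documents. Subjects who stopped in a predecessor study cannot enter the LTE, so Week 52 is close to the earliest stop that leads to follow-up as far as Week 104.

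All of these are event-count figures. The primary measure counts a subject once, so its shift should generally be smaller.

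**The case against.** Several points can be made for the plan.

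- *Defaulting to on-treatment is conservative and applies alike in both arms.* This holds for ambiguous dates. It does not justify overriding a month that excludes on-treatment onset.
- *The rule covers only unresolvable dates, which might mean dates whose period cannot be determined.* On that reading the exception for a month/year before treatment would be redundant. Its presence shows that a known month and year is meant to be used, but the text uses it at one end only.
- *The medication rule is not a worked-out alternative.* This stands. SAP 3.1.7 addresses only a partial date matching the end of treatment, and it also assigns on-treatment. It shows that the SAP compares partial onset dates with the end of treatment elsewhere, and no more.
- *No hypothesis is tested, and on-study summaries are also produced.* True. The on-study tables are immune to this error.

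Two stronger readings are tempting but unsupported. A reader might infer that AEs after the placebo-to-tezepelumab switch enter the placebo rate. The partial-date sentence assigns no arm. Such an AE normally is on-treatment, on tezepelumab, and SAP 2.1.2 limits Randomised Placebo for switchers: "Will include all data from first dose/randomisation in predecessor studies up until switch to tezepelumab". What is missing is only a stated way to place a partial date in the predecessor or LTE period. A reader might also infer that AEs leading to discontinuation are distorted. Such an event must begin before product is stopped, so it cannot plausibly start months after the last dose. Injection site reactions and anaphylaxis are likewise tied to dosing.

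**Conclusion.** The gap is real but narrow. On its literal text, SAP 3.2.2 gives the wrong class to an AE whose known month/year lies wholly after the on-treatment period, contradicts its own post-treatment definition, and adds an event with no matching exposure. The effect is likely under 1% relative for completers. That rests on an assumed 1% to 10% share of partial dates, a constant AE rate, and equal date quality on and off treatment. It is larger for early discontinuers in follow-up, whose number the documents do not give. It would be visible mainly in a rare AESI row. This is a desirable clarification and does not threaten the primary safety conclusion.

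**What to change.** Add a third exception to the partial-date rule in SAP 3.2.2: if the partial onset date (month/year, or year alone) lies wholly after the end of the on-treatment period, the AE is classified as post-treatment. Keep the on-treatment default only where the partial date overlaps the on-treatment period.

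Add one sentence for placebo-to-tezepelumab subjects: a partial date lying wholly within the predecessor period or wholly within the LTE period is placed in that period. Dates that straddle the boundary should not be sent to tezepelumab by default. Under SAP 2.1.2 a switcher's post-switch data belong to neither primary group, so a placebo-period event could drop out of the primary comparison while its placebo days stayed in the denominator.

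The cost is two sentences and a small programming change, with no new data.

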#### 9.4.2 Safety analyses

All safety analyses will be performed on the safety analysis set. Key safety analyses will be repeated using the SAF-LTE analysis set.

The primary objective of the study to evaluate the long-term safety and tolerability of tezepelumab in severe asthma subjects will be assessed through on-treatment AEs (including AESIs, as defined in Section 8.3.8) and SAEs. AEs, AESIs and SAEs will be summarized using exposure adjusted incidence rates (i.e., number of subjects reporting events divided by person-time at risk) to account for the variability in follow-up. CCI

The definition of on-treatment AEs and post-treatment AEs will be defined in the SAP.

The treatment groups for addressing the primary objective will be “Randomized Tezepelumab” and “Randomized Placebo” using the safety analysis set. Supportive analysis of key safety data will be presented for the “Tezepelumab Predecessor+Tezepelumab LTE” and “Placebo Predecessor+Placebo LTE” treatment groups using the SAF-LTE analysis set. Summaries for these 4 treatment groups will be provided overall (Week 0 to Week 104) and by time period

Tezepelumab - D5180C00018

(Week 0 to Week 52/48, Week 52/48 to Week 104). An additional summary of key safety data will be provided for the “Placebo Predecessor+Tezepelumab LTE” treatment group for the SAF-LTE analysis set by time period (Week 0 to Week 52/48, Week 52/48 to Week 104) only.

CCI The “All Tezepelumab” treatment group may additionally be used to report AESIs (rare events) for the safety analysis set. In addition, AESIs may be assessed using the pooled data across the 2 studies.

Laboratory data will be summarized by presenting shift tables using normal ranges (baseline in predecessor study to most extreme post-baseline value) and by presenting summary statistics of observed and change from baseline values (means, medians, quartiles, ranges). The incidence of clinically notable laboratory abnormalities will be summarized.

Further details on additional analyses and presentation of safety data will be provided in the SAP.

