| | Subjects will be assigned according to their randomised treatment. However, if a subject randomised to placebo receives an incorrect treatment, all data after the date the incorrect treatment was received within that time period (predecessor study, LTE study) will be excluded from the analysis, and listed separately. If a subject randomised to tezepelumab receives an incorrect treatment, it will still be regarded as a tezepelumab subject and no data will be excluded after the dose of placebo. Other incorrect dosing, if any, will be handled case-by-case. |
| Full analysis set (FAS) | All subjects who were randomised and received at least 1 dose of IP in any of the predecessor studies, irrespective of their protocol adherence and continued participation in any of the studies, and regardless of their enrolment into this LTE study. |
| | Subjects will be assigned according to their randomised treatment. |
| FAS-LTE | Subjects who were randomised and received at least 1 dose of IP in the LTE study. |
| | Subjects will be assigned according to their randomised treatment. |
| CCI | |
| | |
| | |

The SAF is the primary population for the reporting of the safety data. The FAS is the primary population for the reporting of efficacy data. The SAF-LTE, FAS-LTE will be used for supportive analyses only.

The main summaries of demographics and baseline characteristics will be based on the SAF and SAF-LTE analysis sets, but additional summaries may be provided as detailed in Section 4.2.

In addition to the analysis sets defined above, LTE analysis set will be defined as all subjects who signed the informed consent for the LTE study. This analysis set will be used for reporting the disposition data during the LTE period.

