4.5 Safety and tolerability

4.5.1 Adverse events

AEs will be summarised separately for the on-treatment and on-study periods as defined in Section 3.2.2 unless stated otherwise. All AE summaries will be presented by analysis set and treatment groups as follows:

- SAF (Randomised Tezepelumab and Randomised Placebo), overall only
- SAF-LTE (Tezepelumab Predecessor+Tezepelumab LTE and Placebo Predecessor+Placebo LTE), overall and by time period
- SAF-LTE (Placebo Predecessor+Tezepelumab LTE), predecessor and LTE periods

All AEs will be listed for the SAF-LTE analysis set. AEs occurring during the screening/runin period or occurring post-treatment will be highlighted with an asterisk in the listing, but
not summarised separately. In addition, for subjects with a delay between the predecessor
study EOT visit and LTE study Visit 1, a listing of AEs starting more than 33 days after the
last dose of IP in the predecessor study but prior to Visit 1 in the LTE study will be provided.
A further listing of AEs occurring between the LTE study Visit 1 and the date of first dose in
the LTE study will be provided for those subjects who do not receive their first dose of IP in
the LTE study at Visit 1 of the LTE study. Information related to the outcome of any
pregnancies will also be listed for the SAF-LTE analysis set.

For each of the summaries below, the following will be included:

- Number and percentage of subjects reporting at least one AE.
- Exposure adjusted incidence rates (as defined in Section 3.2.2) per 100 subject-years

An overall summary table will be produced showing the following categories: any AEs, serious adverse events (SAEs), AEs with a fatal outcome, and AEs leading to discontinuation of IP (DAEs).

All AEs will be summarised by system organ class (SOC) and preferred term (PT) assigned to the event using the MedDRA dictionary. For each PT, for the number of subjects reporting at least one occurrence of the event, subjects with multiple occurrences of the same PT will only be counted once for the calculation of incidence rates.

Similar summaries by SOC and PT will also be presented for:

- SAEs
- Fatal AEs
- DAEs on-treatment period only

- DAEs causally related to IP on-treatment period only
- SAEs leading to discontinuation of IP on-treatment period only
- Each AESI category separately on-treatment period only

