6 CHANGES OF ANALYSIS FROM PROTOCOL

• A new analysis set "LTE analysis set" has been added to the SAP to show the full disposition of subjects from the predecessor studies, and to allow for the possibility that subjects may be enrolled or randomised in the LTE study but do not take IP in the LTE study.

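### The primary AE incidence rate keeps counting exposure after a subject's first event, and planned follow-up is longer on tezepelumab, so common AEs read too low for tezepelumab when the true hazards are equal and constant or falling

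*SAP*

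**What the plan says.** The protocol's primary outcome measure is the exposure-adjusted incidence rate of AEs and SAEs over 104 weeks. Protocol 9.4.2 describes "exposure adjusted incidence rates (i.e., number of subjects reporting events divided by person-time at risk", chosen to allow for variable follow-up. It does not define time at risk.

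SAP 3.2.2 gives the working definition: "exposure adjusted incidence rates will be defined as the number of subjects reporting adverse events divided by total exposure duration for that treatment group". Each subject's exposure runs from the start to the end of the on-treatment or on-study period, and nothing stops it at the first event. On the numerator the same section says "A subject will either be considered to have no events of the type being summarised, or one or more occurrences of that event".

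SAP 2.1.2 sets the two primary groups. Randomised Tezepelumab is followed from the predecessor study to the end of the LTE. For Randomised Placebo subjects who cross over, the rule is "Will include all data from first dose/randomisation in predecessor studies up until switch to tezepelumab". Placebo rollovers are re-randomised 1:1, so about half are cut at Week 52 (D5180C00007) or Week 48 (D5180C00009).

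On the time split, protocol 9.4.2 says of the two primary and two supportive groups: "Summaries for these 4 treatment groups will be provided overall (Week 0 to Week 104) and by time period". SAP 4.5.1 instead specifies "SAF (Randomised Tezepelumab and Randomised Placebo), overall only", and Table 10 of the SAP agrees. SAP Section 1 says changes from the protocol are described in Section 6. The one change listed there is a new LTE analysis set, which "has been added to the SAP to show the full disposition of subjects from the predecessor studies".

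**The concern.** A subject who has an early event cannot add to the numerator again but goes on adding to the denominator. The rate therefore estimates F(T)/T, where F is the cumulative probability of a first event by time T. With a constant or falling hazard, F(T)/T declines as T grows, so the arm followed longer shows the lower rate even when the drug has no effect. Here the longer-followed arm is tezepelumab, and the imbalance comes from the design rather than from chance dropout.

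The primary safety comparison could then show an apparent advantage for tezepelumab, or hide a true excess, for any AE and for frequent SOCs and PTs. No hypothesis is tested, so the harm is a misleading descriptive comparison, not an inflated type I error.

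The dropped by-period tables matter for the same reason. In the predecessor period both randomised arms have the same planned length, so that table would be free of this artefact. It is the main display lost: in the LTE period the Randomised groups are essentially the Teze+Teze and Pbo+Pbo subjects, who keep their by-period tables.

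**Working it through.** **The plan's own figures.** With equal rollover from the two arms, LTE allocation is (1 + 0.5) : 0.5 = 3:1, and 860 + 115 = 975. Both match the plan. The expected subject-years, dropout rates and example confidence intervals are blacked out and cannot be reproduced.

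**Inputs**
- Rollover: 0.90 × 0.90 = 0.81 in each arm (protocol 9.2, SAP 1.3).
- Placebo rollovers who switch: one half, so 0.405 stay on placebo (SAP 1.2).
- Planned lengths: 52 + 52 weeks (D5180C00007) or 48 + 56 weeks (D5180C00009), with 52 weeks taken as one year.
- AE frequency: about 66% in each arm over 50 weeks in the Phase 2b study (protocol 2.2), used as an illustration.
- Assumptions: same hazard in both arms, no LTE dropout, and non-rollovers followed to the end of the predecessor period.

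**Planned follow-up, D5180C00007**
- Tezepelumab: 0.81 × 2 + 0.19 × 1 = 1.81 years.
- Placebo: 0.405 × 2 + 0.595 × 1 = 1.405 years.

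**Base case, constant hazard**
- h = −ln(1 − 0.66) / (50/52) = 1.122 per year, so F(1) = 0.674 and F(2) = 0.894.
- Tezepelumab: (0.81 × 0.894 + 0.19 × 0.674) / 1.81 = 0.471.
- Placebo: (0.405 × 0.894 + 0.595 × 0.674) / 1.405 = 0.543.
- Ratio 0.867 where the truth is 1.
- D5180C00009 (48/52 year in place of 1): 0.472 vs 0.549, ratio 0.859.

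**Ratio shown, by constant hazard (D5180C00007)**

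| Hazard per year | True ratio 1.0 reads | True hazard ratio 1.2 reads |
|---|---|---|
| 0.03 | 0.995 | – |
| 0.05 | 0.99 | – |
| 0.1 | 0.98 | 1.16 |
| 0.3 | 0.96 | 1.09 |
| 0.6 | 0.92 | 1.01 |
| 1.12 | 0.87 | 0.91 |
| 2.0 | 0.82 | – |

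**Sensitivity, no true difference**
- If the 10% who do not complete the predecessor study stop at 0.25 to 0.75 years, the base case reads 0.86.
- Varying LTE dropout (5 to 20%) and rollover (70 to 90%) by arm at this AE frequency gives 0.83 to 0.91.
- Year-2 hazard doubled: 1.10 at 0.1 per year (reversed), but still 0.89 at 1.12 per year.
- Year-2 hazard halved: 0.90 at 0.1 per year.

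**What a first-onset denominator would do.** Replace each T by the integral of S(t) from 0 to T, where S = 1 − F.
- Constant hazard: ratio 1.00.
- Gamma frailty, S(t) = (1 + vHt)^(−1/v), with H set so that S(50/52) = 0.34: for v = 0.5, 1 and 2 the ratio is 0.96, 0.93 and 0.89, against 0.85, 0.83 and 0.82 under the SAP rule.
- At 0.1 per year: 1.12 if the year-2 hazard doubles (SAP rule 1.10) and 0.91 if it halves (SAP rule 0.90).

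So the change removes most of the distortion for common events but does little for uncommon events with time-varying hazards. Those need periods of equal planned length.

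**The case against.** The strongest case on the other side is about weight:

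- **Crude percentages appear in the same tables.** In the base case they are 85% vs 76%, leaning against tezepelumab, so a reader would see two measures disagree. That makes unnoticed false reassurance less likely. But the percentages are distorted by the same unequal follow-up and do not correct the rate.
- **The SAF-LTE comparison has equal planned follow-up**, overall and by period, and the protocol's caution about selection is aimed chiefly at asthma-control measures. This is real mitigation. Still, SAP 2.1 says "The SAF-LTE, FAS-LTE will be used for supportive analyses only", and selection on tolerability remains possible.
- **AESIs also get event-count rates**, which lack the once-only numerator. These do not cover the any-AE or SOC/PT tables.
- **The predecessor-period table may largely repeat the predecessor studies' own safety reports.** That is plausible but cannot be checked here, and the departure from the protocol would still need listing.
- **The SAP does state its denominator**, and the protocol leaves presentation detail to the SAP. What remains on that point is a mismatch with the protocol's wording about time at risk.
- **The size rests on a different study's AE frequency and on zero LTE dropout.** Agreed. The dropout and rollover variations move the ratio between 0.83 and 0.91 without removing the effect.
- **A first-onset denominator is only a partial cure.** Also agreed, which is why it is paired with the by-period tables.

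None of these removes the mechanism or the undeclared departure.

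**Conclusion.** The concern holds and should be fixed. As defined, the primary AE rate does not adjust for the unequal follow-up that the design creates. For an AE category as common as any AE in the Phase 2b study, equal arms would display a ratio of about 0.87 (D5180C00007) or 0.86 (D5180C00009), and a true hazard ratio of 1.2 would display as 0.91. These figures assume equal rollover by arm, a constant hazard and no LTE dropout.

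The effect is limited to common categories. Under a constant hazard it is about 2% at 0.1 per year and negligible for rare AESIs. It is likewise negligible for SAEs if they are as rare, but the documents give no SAE rate. The direction is reliable for common events; for uncommon events a rising hazard reverses it.

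Confidence is high in the mechanism and direction for common events, lower in the exact size in this trial. Separately, and without any modelling, the SAP omits by-period AE summaries that the protocol promises for the primary groups and does not declare the omission.

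**What to change.** 1. In SAP 3.2.2, define the incidence-rate denominator for each AE category, SOC and PT as time from first dose to first onset of that event, or to the end of the period if there is none (for a by-period table, counted from the start of that period). Bring the protocol and SAP wording into line.
2. In SAP 4.5.1 and Table 10, restore the predecessor-period and LTE-period AE summaries for Randomised Tezepelumab and Randomised Placebo on the safety analysis set. The predecessor-period table matters most: equal planned length also deals with heterogeneity between subjects and with hazards that change over time.
3. List any remaining departure from protocol 9.4.2 in SAP Section 6.

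The cost is SAP wording and modest programming. Onset dates and period categories are already derived under SAP 3.2.2, and SAP 4.5.2 already splits the Hy's law plots by period on the same analysis set. Reported rates for common AEs will be numerically larger than under the present definition, which the study report should explain.
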